#### **1.11.7. Other Risks**

Possible risks related to the administration of the study drug and/or as a consequence to phlebotomy may include hematoma or bruising.

#### **1.11.8. Other Safety Monitoring**

Additional safety monitoring will include the parameters of adverse events (AEs), physical examination, vital signs, and clinical laboratory parameters (including urinalysis, hematology, gamma-glutamyl transferase [GGT], glutamate dehydrogenase [GLDH], prothrombin time/activated partial thromboplastin time [PT/aPTT], creatine kinase, amylase, and chemistry) and Columbia Suicide Severity Rating Scale (C-SSRS). Laboratory monitoring will also be performed to detect ADA and NAb.

## 1.12. Summary of Risk Benefit

Study B5161002 is the first therapeutic study being conducted in pediatric subjects with DMD. The drug may demonstrate pharmacologic activity in subjects.

In view of the initial clinical evidence of safety and the monitorable nature of key nonclinical toxicological findings, data support an acceptable risk profile for PF-06252616 in the current study and support a favorable benefit-risk profile in the indication of DMD. Authorities will be kept informed of any additional data (eg, results from clinical studies) which may affect the assessment of the risk/benefit ratio for PF-06252616.

## 2. STUDY OBJECTIVES AND ENDPOINTS

### 2.1. Objectives

#### 2.1.1. Primary Safety and Efficacy

- To determine the safety and tolerability of multiple ascending repeat IV doses of PF-06252616 in ambulatory boys with DMD.
- To demonstrate the efficacy of treatment with IV doses of PF-06252616 based on an observed mean change from baseline on function (4 Stair Climb) as compared to placebo following 49 weeks of treatment.

#### 2.1.2. Secondary

- To characterize the effects of PF-06252616 on muscle strength and other functional assessments compared to placebo.
- To evaluate the PD activity of PF-06252616 based on the percent change of muscle volume from baseline as compared to placebo.
- To evaluate the PD profile of PF-06252616 based on GDF-8 (myostatin) modulation in blood.
- To characterize the PK profile of PF-06252616.
- To evaluate the immunogenicity of PF-06252616.
- To characterize the long-term effects following approximately 2-years of treatment with PF-06252616 on functional assessments compared to historical control.
- To characterize the effects of PF-06252616 on muscle strength and functional assessments compared to placebo in subset of subjects who may demonstrate a rapid disease decline and with relatively low variability over a one-year period.

#### 2.1.3. Exploratory

- To evaluate biomarkers that may be informative in demonstrating the pharmacologic effect of PF-06252616.

- To evaluate biomarkers that may be informative for monitoring hepatic liver injury in the setting of dystrophic muscle.
- To evaluate the Functional Health Status.
- To evaluate long term safety of PF-06252616 in subjects treated for >1 year.
- To evaluate duration of treatment response following withdrawal and/or continuation of treatment for >1 year.
- To evaluate response in a delayed treatment group (Sequence Group 3, Period 2).

## **2.2. Endpoints**

### **2.2.1. Primary Safety-Based on Data from Period 1**

- Incidence of dose limiting or intolerability treatment related AEs by Week 49.
- Incidence, severity and causal relationship of treatment emergent AEs (TEAEs) and withdrawals due to TEAEs by Week 49.
- Incidence and magnitude of abnormal laboratory findings (clinical laboratory tests [hematology, chemistry, GGT, GLDH, PT, aPTT, creatine kinase, amylase, serum ferritin, serum iron, Total Iron Binding Capacity (TIBC), % transferrin saturation, hormone [luteinizing hormone [LH], follicle stimulating hormone [FSH], thyroxine [T4], thyroid stimulating hormone [TSH], fecal occult and urinalysis) by Week 49.
- Abnormal and clinically relevant changes in liver MRI by Week 45 and physical examinations (including nose and throat mucosal exam and Tanner stage), weight, vital signs, ECG, cardiac MRI or echocardiogram measured LVEF (and other exploratory cardiac endpoints), DXA-spine (bone mineral density), x-ray (hand and wrist for bone age evaluation) and C-SSRS (See [Appendix 1](#) and [Appendix 2](#)) parameters by Week 49. Cardiac MRI with gadolinium is the preferred method for cardiac imaging. If the subject has a contraindication to gadolinium, cardiac MRI without gadolinium will be acceptable. Echocardiogram may be substituted if it is not possible to perform cardiac MRI.

### **2.2.2. Primary Efficacy-Based on Data from Period 1**

- Mean change from baseline on the 4SC as compared to placebo by Week 49.

### **2.2.3. Secondary Endpoints-Based on Data from Period 1 and 2**

#### **2.2.3.1. Strength and Function**

- Mean change from baseline as compared to placebo on function tests including, Forced Vital Capacity (FVC), Northstar Ambulatory Assessment (NSAA), range of motion (ROM), Performance of Upper Limb (PUL), 6MWD at Week 17, 33 and 49. Mean change from baseline as compared to placebo on the 4 SC at Week 17 and 33.

- Mean change from baseline as compared to placebo on muscle strength by myometry at Week 17, 33 and 49.
- In subject randomized to Sequence 1, mean change from baseline as compared to historical control on functional tests including, 4SC, 6MWD, FVC, NSAA at Week 97.
- In a pre-specified subset of subjects who may demonstrate a rapid disease decline and with relatively low variability, the mean change from baseline as compared to placebo on function tests including, 4SC, FVC, NSAA, PUL, 6MWD at Week 17, 33 and 49. The definition of this subgroup will be detailed in the Statistical Analysis Plan (SAP).
- In a pre-specified subset of subjects who may demonstrate a rapid disease decline, the mean change from baseline as compared to placebo on muscle strength at Week 17, 33 and 49.

#### 2.2.3.2. Pharmacodynamic

- Mean percent change as compared to placebo in thigh muscle volume as measured on MRI by Week 17, 33 and 49. Within subject change from baseline in thigh muscle volume through Week 97.
- Noncompartmental GDF-8 parameters such as  $AUC_{\tau(GDF-8)}$ ,  $C_{GDF-8(0)}$ ,  $C_{max(GDF-8)}$ ,  $T_{max(GDF-8)}$ ,  $C_{trough(GDF-8)}$ , and  $C_{av(GDF-8)}$ , may be determined.

#### 2.2.3.3. Pharmacokinetic

Noncompartmental PK parameters will be derived from serum PF-06252616 concentration data for the following subjects and visits.

- All subjects receiving active drug:  $C_{max}$ ,  $T_{max}$ , and  $C_{trough}$  for all visits with PF-06252616 dosing.
- All subjects receiving active drug in Period 1 followed by placebo in Period 2 (Sequence 2): terminal  $t_{1/2}$  for Visit 19 (last dose in Period 1) using concentration data from samples collected during placebo treatment in Period 2.
- Subjects with additional PK sampling receiving active drug in Period 1:  $AUC_{\tau}$  and  $C_{av}$  for Visits 3, 9, and 15 (first dose of each dose escalation level);  $AUC_{\tau}$ ,  $C_{av}$ , and CL for Visits 7, 13, and 19 (last dose of each dose escalation level); for subjects in Sequence 2, also  $V_{ss}$  for Visit 19.

#### 2.2.3.4. Immunogenicity

Incidence of ADA and NAb development by Week 97.

## **2.2.4. Exploratory Endpoint-Based on Data from Period 1 and 2**

### **2.2.4.1. Pharmacologic**

- Mean percent change from baseline as compared to placebo in lean body mass by whole body DXA by Week 17, 33 and 49. Within subject change from baseline in lean body mass through Week 97.
- Changes from baseline in muscle quality and fat fraction as compared to placebo as measured by T2-mapping and Dixon MRI Week 17, 33 and 49. Within subject change from baseline in T2-mapping and Dixon MRI through Week 97. Depending on the imaging capabilities at each site, this data may only be collected at a subset of sites.
- Quantification of changes as measured by blood biomarkers (pharmacogenomic and liver).

### **2.2.4.2. Functional Health Status**

Changes from baseline in the Pediatric Data Outcomes Collection Instrument (PODCI) score as compared to placebo by Week 17, 33 and 49. Within subject change from baseline in the PODCI through Week 97. See [Appendix 3](#).

### **2.2.4.3. Long Term Safety-Based on Data from Period 2**

In subjects randomized to Sequence 1, long term safety will be evaluated within subjects as compared to baseline for all safety endpoints previously described through Week 97.

### **2.2.4.4. Duration of Treatment Response-Based on Data from Period 2**

In subjects randomized to Sequences 1 and 2, duration of treatment response will be evaluated within subjects as compared to baseline for all efficacy (function and strength), pharmacologic and PD endpoints previously described through Week 97.

### **2.2.4.5. Response in a Delayed Treatment Group-Based on Data from Period 2**

In subjects randomized to Sequence 3, treatment response will be evaluated within subjects as compared to baseline for all efficacy (function and strength), pharmacologic and PD endpoints previously described through Week 97.

## **3. STUDY DESIGN**

### **3.1. Study Overview**

This is a Phase 2 randomized, 2-period, double-blind, placebo-controlled, multiple ascending dose study to evaluate the safety, efficacy, PK and PD of PF-06252616 administered to ambulatory boys diagnosed with DMD. Three IV infused dose levels will be investigated in a within subject dose escalating fashion.

PF-06252616 dose levels:

- 5 mg/kg
- 20 mg/kg
- 40 mg/kg

Depending on safety and PK data availability, alternative dose levels will be available and may be evaluated instead of or in addition to the planned dose levels. In Period 2, dosing may be adjusted based on the emerging safety and/or efficacy data.

Approximately 105 eligible subjects will be randomly assigned to 1 of 3 sequence groups and receive investigational product for approximately 96 weeks (2 treatment periods of approximately 48 weeks each) stratified by their baseline time to complete the 4 SC (either  $\leq$  or  $>8$  seconds).

**Sequence 1 (n=35):**

Period 1: Active treatment (PF-06252616) within subject dose escalation (5, 20 and 40 mg/kg)

Period 2: Active treatment (PF-06252616) at the maximum tolerated dose in Period 1

**Sequence 2 (n=35):**

Period 1: Active treatment (PF-06252616) within subject dose escalation (5, 20 and 40 mg/kg)

Period 2: Placebo

**Sequence 3 (n=35):**

Period 1: Placebo

Period 2: Active treatment (PF-06252616) within subject dose escalation (5, 20 and 40 mg/kg)

Each dose level will be explored in a dose escalating fashion within subjects, starting with the lowest dose. At each dose level, dosing will be administered over a 2-hour IV infusion every 4 weeks for a total of 16 weeks (4 doses). Dose escalation within a subject will occur following review of all available safety data through the planned fourth dose within each dose level. For example, in Period 1, there are three times when individual safety data will be reviewed for a determination of dose adjustment, at Week 13, Week 29 and Week 45 (every 4 months). In Period 2, there are two times when individual safety data are reviewed for a determination of dose adjustment, at Weeks 61 and 77 (every 4 months). Subjects will move from Period 1 to Period 2 without a pause between periods.

[figure not shown]
Subjects who complete this study through Week 97 may be invited to participate in an open-label-extension (OLE) study. Subjects, who have had a positive test result for ADA at any point during the study, *may* be asked to complete additional immunogenicity testing if warranted by other clinical safety findings prior to joining an extension study.

During the study, additional visits will be required to fully characterize PK and safety when subjects would not otherwise be returning for study drug administration. In order to limit the burden of the additional PK/safety assessments, only the first 12 subjects enrolled in the study will be asked to complete these additional PK visits. At each dose level, the first 12 subjects will be asked to return for testing 1 week after the first dose within each level and once again at 1 week after the last dose at each dose level. The additional PK/safety assessments will occur 6 times in Period 1. No additional visits would be required for these subjects in Period 2.

Exposure from the first 12 subjects will be reviewed to confirm that the exposure in the pediatric population is consistent with model predictions from the healthy adult volunteer study. This will occur following at least one dose at the 5 mg/kg dose level and will occur again following at least one dose at 20 mg/kg dose level. Should there be any clinically relevant differences in exposure versus those predicted; a dose adjustment may be made as agreed with the E-DMC. This analysis will be performed by a group of unblinded Clinical Pharmacology scientists not directly involved in the day to day conduct of the study. It is planned that recruitment would continue during this evaluation period.

The study will remain double-blinded until the time of the primary analysis for safety and efficacy (after the last enrolled subject completes 49 weeks). At that time, a limited number of study team members will be unblinded to the treatment assignments. The sites (with the exception of unblinded site personnel eg, the pharmacist) and the subjects will remain blinded to their study treatment through the conclusion of the study.

The following is a schematic of the study design.

Note: Sequence 1, Period 2 demonstrates subjects continuing on the maximum tolerated dose from Period 1 for each individual subject, as per the dose adjustment criteria (Table 2). SCRN=Screening, PBO=Placebo, W=Weeks

### **3.2. Duration of Subject Participation**

Subjects' participation will begin during the screening period (up to 6 weeks) followed by two dosing periods (48 weeks each) and 2 final study visits (ending 12 weeks after the last study dose). Subjects, who are enrolling in the OLE study, will only be required to return for 1 final study visit at Week 97. Subjects will return to the site monthly for study drug administration (24 visits) as well as completion of safety and efficacy assessments.

For the first 12 subjects enrolled who are undergoing the additional PK testing, a total of 34 visits are required. The remaining subjects will be expected to attend 28 visits. The total time on study for all subjects will be approximately 105 weeks (26 months including screening).

In order to assure consistency in assessment collection, visits that include functional assessments and imaging assessments (DXA and thigh MRI) will be collected over a 2-day period within the study visit window. In the case where subjects are traveling from a distance, the site will offer nearby overnight accommodations.

Per the local requirements in Japan, all Japanese subjects will be hospitalized for an overnight observation following the first and second treatment (Day 1 and 29).

### **3.3. Approximate Duration of Study**

The study is estimated to complete in approximately 5 years allowing for 30 months of enrollment and 26 months on study.

The end of the study will be the last visit of the last subject for purposes of closing out sites, informing the institutional review board/ethics committee (IRB/EC), and ceasing to send Council for International Organizations of Medical Sciences (CIOMS) reports.

### **3.4. Planned Number of Subjects**

A minimum of 105 randomized subjects will participate in multiple centers and countries worldwide. In order to assure adequate enrollment, a sufficient number of subjects may be screened. If there are no safety issues, additional subjects may be enrolled prior to the time of the interim analysis. These additional subjects may help off-set any unforeseen variability that may occur outside the presumed standard deviation for this age group.

### **3.5. Safety Monitoring, Individual Dose Escalation and the E-DMC**

Individual dose escalation decisions will be conducted for each subject by the Investigator, sponsor Medical Monitor and a Designated Reviewer. This process will occur from time of the first subject being enrolled and continue until the time of the IA (or sooner as determined by the E-DMC's review of unblinded data). At that time, if adequate safety has been demonstrated at each dose level as determined by an External Data Monitoring Committee (E-DMC), subsequent dose escalation will occur without confirmation of the individual safety data prior to dose escalation.

From the time of study initiation through completion of the study, the sponsor will conduct routine safety monitoring of the blinded data per the safety review plans. In addition, the E-DMC will review unblinded safety data. The E-DMC may determine if it is necessary to close or adjust a dose level within the study or continue with individual level dose escalation review.

In the event that the E-DMC determines that adequate safety has been established at each dose level (following the IA or sooner), they will also consider if the requirement for liver MRI can be reduced to an annual safety assessment (based on normal findings on the liver MRI).

Following the interim analysis, if the E-DMC makes a recommendation to the sponsor management to modify or terminate the study based on establishing the efficacy and safety of PF-06252616, the sponsor management will review the recommendation with regulatory agencies prior to making any changes to the study design, including termination of the study.

### **3.5.1. Individual Subject Dose Adjustment and Stopping Rules**

The individual dose adjustment will be determined by three parties including the Investigator, sponsor Medical Monitor and a Designated Reviewer.

The dose adjustment criteria described in [Table 2](#) will be used to determine if the dosing or dose level should be:

- Escalated to the next dose level
- Maintained at the current dose level
- Reduced to a lower dose level, or
- Stop dosing.

Following the planned fourth dose within each dose level, all available safety data for an individual subject will be reviewed to determine the appropriate dose adjustment. The Investigator will confirm the number of doses received within the dose level and review all the available safety data along with the sponsor Medical Monitor with the exception of the serum iron indices (serum iron, serum ferritin, TIBC, % transferrin saturation) and the liver MRI results. Findings from the serum iron indices and the liver MRI may inadvertently unblind the Investigator and the sponsor Medical Monitor to the subject's treatment assignment, therefore results from these tests will not be available to the sites or sponsor Medical Monitor for review. Instead, an unblinded Designated Reviewer will review the liver MRI results to monitor for potential iron accumulation. The E-DMC will be unblinded to the serum iron indices and liver MRI results to provide an ongoing safety review of these data.

The Investigator and sponsor Medical Monitor, if necessary will meet to discuss any safety issues and then provide a single recommendation to the unblinded Designated Reviewer who will be separately monitoring the liver MRI results. The Designated Reviewer will collect the safety confirmation from the Investigator and sponsor Medical Monitor and apply the criteria from Table 2 to determine the dose adjustment action. The dose adjustment will then be applied to the subject's assigned treatment, accordingly.

**Table 2. Criteria to Determine Dose Adjustment within Individual Subjects**

Dose Adjustment Decision	Criteria
Increase Dose Level	E-DMC has not closed the next higher dose level and Subject received $\geq 3$ doses within a the current dose level and Investigator and sponsor Medical Monitor indicate that the current dose level is safe and Designated Reviewer indicates that the liver iron content estimate as determined by R2* value is within the normal range a,d .
Maintain Dose Level	E-DMC indicates that the next higher dose level is closed and/or Subject received $< 3$ doses received within a dose level and Investigator and sponsor Medical Monitor indicate that the current dose level is safe and Designated Reviewer indicates that the liver iron content estimate as determined by R2* is in the normal range a,d .
Reduce Dose Level	E-DMC indicates that the current dose level is closed and the subject is not at the lowest dose level or Subject is not at the lowest dose level and Investigator and sponsor Medical Monitor indicate that the current dose is safe and Designated Reviewer indicates that the liver iron content estimate as determined by R2* value is above the normal range b,d .
Stop Dosing	E-DMC indicates that the current dose level is closed and the subject is at the lowest dose level or Investigator and sponsor Medical Monitor indicate that the current dose is not safe or Designated Reviewer indicates that the liver iron content estimate as determined by R2* value is above the normal range b,d and the subject is at the lowest dose level or Designated Reviewer indicates that the liver iron content estimate as determined by R2* value is within mild overload range c,d .

a. R2\* normal range is  $\leq 75$  Hz at 1.5 T or  $R2^* \leq 139$  Hz at 3.0 T  
 b. R2\* above normal range is  $> 75$  Hz and  $\leq 190$  Hz at 1.5 T or  $R2^*$  is  $> 139$  Hz and  $\leq 369$  Hz at 3.0 T  
 c. R2\* mild overload range is  $R2^* > 190$  Hz at 1.5 T or  $R2^* > 369$  Hz at 3.0 T  
 d. Storey et al, 2007; Wood et al, 2005; Hankins et al, 2009).

In order to maintain the treatment blind, all subjects regardless of treatment assignment will undergo review for dose adjustment. Subjects who are receiving placebo will have the decision criteria applied, as if they are at the lowest dose level.

The results of the dose adjustment decision (increase, maintain or reduce) *will not* be communicated to the investigator or sponsor medical monitor at any time.

If the Designated Reviewer determines that the subject must stop dosing, he/she will notify the sponsor Medical Monitor who will be responsible for informing the Investigator. In this case, the Designated Reviewer may provide the results of the liver MRI (or iron indices) to the sponsor Medical Monitor. The treatment assignment however, will not be provided.

If dosing is stopped, subjects will continue to be followed for resolution of the safety finding or until a new baseline is established. At any time during the study, either the Investigator and/or sponsor Medical Monitor may determine a safety issue has occurred and it is in the best interest of the subject to stop dosing. In this case, the sponsor Medical Monitor may not overrule the Investigator's decision, nor will the Investigator overrule the sponsor Medical Monitor's decision.

If the E-DMC determines that a dose level should be closed, following their unblinded review of all safety data, no other subjects will be escalated to that dose level. Subjects who are currently dosing within that dose level will be advised by the E-DMC to reduce their dose level.

Subjects in Sequence 2, Period 2, and Sequence 3 Period 1 (who are assigned to placebo), will have dosing terminated should they meet any of the criteria described in [Table 2](#) for "Stop Dosing".

Subjects in Sequence 1 will be treated with their maximum tolerated dose level from Period 1 when they enter Period 2. They will not be escalated to additional higher dose levels in Period 2. For example, if in Period 1, a subject's maximum tolerated dose is 20 mg/kg, they will not be escalated up to 40 mg/kg in Period 2. Although they will not escalate in Period 2, they may have their dose reduced or stop dosing based on the criteria in [Table 2](#).

Subjects, who plan to enroll in the OLE study, will have their *maximum tolerated dose* from study B5161002 be provided by the Designated Reviewer following Week 93 in order to continue on the same dose level in the OLE study without unblinding their treatment assignment in the B5161002 study.

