**Table 4. Period 2 Dosing Schedule**

Dosing Week	49	53	57	61	65	69	73	77	81	85	89	93
Sequence 1 PF-06252616 Dose	40 mg/kg (or maximum tolerated dose per each subject) once every 4 weeks											
Sequence 2 Placebo Dose	0 mg/kg once every 4 weeks											
Sequence 3 PF-06252616 Dose	5 mg/kg once every 4 weeks			20 mg/kg once every 4 weeks			40 mg/kg once every 4 weeks					

Note: Sequence 1 in this example shows all subjects tolerating the maximum dose level.

Following demonstration of tolerance at a lower dose, if subjects are unable to tolerate higher doses, their dose level may be reduced by a level at the time of dose escalation. Subjects in Sequence 1 will be treated at their maximum tolerated dose level from Period 1 when they enter Period 2 and they will not be escalated to additional higher doses during Period 2. Subjects in Sequence 3 will receive active drug in Period 2 in accordance with the dose adjustment criteria.

Subjects should be administered the investigational product within the visit window according to the schedule of activities. If a dosing visit cannot be conducted within the visit window, attempts should be made to bring the subject back for dosing as soon as possible; however the dosing must not occur within 2 weeks prior to the next scheduled dose. If the subject cannot return for dosing in this timeframe, the dose should be missed and the next visit should be conducted per the [Schedule of Activities](#).

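### At Week 29 the same raised liver R2* stops a placebo boy visibly but only reduces an on-schedule active boy silently, so a stop known to be in that range points to placebo

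*Protocol*

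**What the plan says.** Protocol 3.5.1 puts every boy, active or placebo, through the same dose-adjustment review so that the blind holds. The next sentence adds: "Subjects who are receiving placebo will have the decision criteria applied, as if they are at the lowest dose level". It sets no time limit. Protocol 3.1 says that in Period 1 "individual safety data will be reviewed for a determination of dose adjustment, at Week 13, Week 29 and Week 45".

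Table 2 treats an R2* above normal but below mild overload (above 75 and up to 190 Hz at 1.5 T; above 139 and up to 369 Hz at 3.0 T; here called the band) according to dose level. The Reduce row requires: "Subject is not at the lowest dose level and Investigator and sponsor Medical Monitor indicate that the current dose is safe". The Stop row covers the same band under one condition and then turns to mild overload: "and the subject is at the lowest dose level or Designated Reviewer indicates" a mild-overload value.

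Decisions to increase, maintain or reduce will not "be communicated to the investigator or sponsor medical monitor at any time". A stop goes from the Designated Reviewer to the Medical Monitor and on to the Investigator. In that case "the Designated Reviewer may provide the results of the liver MRI (or iron indices) to the sponsor Medical Monitor", although the treatment assignment is not given. The same section explains why these data are otherwise withheld: "Findings from the serum iron indices and the liver MRI may inadvertently unblind the Investigator and the sponsor Medical Monitor".

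Table 3 has active boys at 20 mg/kg from Week 17 to Week 29, and Protocol 6.7 schedules a liver MRI at Visit 13 (Day 197, Week 29).

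**The concern.** At Week 29 one scan result has two consequences. A placebo boy in the band is handled as if at 5 mg/kg, so he is stopped and the stop is announced. An active boy on schedule at 20 mg/kg goes back to 5 mg/kg and no one blinded hears of it. The protocol says that the assignment is not disclosed with a stop, but does not consider what the stop itself discloses.

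The blind of the Medical Monitor is at stake, for boys who still have four Period 1 infusions to come (Weeks 33 to 45). Reporting is a second issue. SAP 6.6 counts discontinuations by treatment. If R2*-triggered stops enter that count, the same Week 29 value adds to the placebo column and not to the active one.

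**Working it through.** The plan gives no figure for this, so there is none to reproduce.

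**Inputs**
- Allocation in Period 1: 70 active, 35 placebo (Protocol 9.1).
- f = share of active boys still at 5 mg/kg at Week 29, for example after fewer than three doses. Not given; assumed.
- k = ratio of band rates, active to placebo. Not given; assumed.
- p = placebo band rate per review. Not given; it cancels from the shares.
- s = chance that a raised R2* is still raised at the next scan. Not given; assumed.

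**Placebo share among band stops**
- Week 13. All active boys are at 5 mg/kg and the arms are handled alike. Share = 35/(35 + 70k): 33% at k = 1, 14% at k = 3.
- Week 29. Only active boys still at 5 mg/kg can be stopped in the band. Share = 35/(35 + 70fk).
  - f = 0: 100% for any k.
  - f = 5%: 35/38.5 = 91% at k = 1; 35/45.5 = 77% at k = 3.
  - f = 10%: 35/42 = 83% at k = 1; 35/56 = 63% at k = 3.
- Week 45. Active boys reduced at Week 29 are now at 5 mg/kg and are stopped if still raised. Taking f = 0, share is about 35p/(35p + 70kps) = 1/(1 + 2ks). At k = 1 this is 67%, 50% and 36% for s = 0.25, 0.5 and 0.9. At k = 3 it is 40%, 25% and 16%.

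**If the R2* value is not released**, mild-overload stops mix in, and these occur at any dose. Take f = 0, no mild overload on placebo, and an active mild-overload rate equal to 10%, 25% or 50% of the placebo band rate. The share is then 35/(35 + 7) = 83%, 35/(35 + 17.5) = 67% or 35/(35 + 35) = 50%.

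**How many boys.** Expected Week 29 placebo stops, after Week 13 stops, are 35(1 − p)p, and the chance of at least one is 1 − (1 − p)^(35(1 − p)).
- p = 1% to 5%: 0.35 to 1.66 stops; chance of any 29% to 82%.
- p = 0.1% to 0.5%: 0.03 to 0.17 stops; chance of any 3% to 16%.

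With all active boys escalated, the silent reductions number 70(1 − kp)kp. For p = 1% to 5% that is 0.7 to 3.3 at k = 1 and 2.0 to 8.9 at k = 3, with no active band stops.

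**The case against.** The strongest reply is that little follows from this. R2* need not be released, and if it is, 3.5.1 sends it only to the Medical Monitor. The Investigator hears of the stop alone, which could equally be mild overload. The stair climb is timed by a physiotherapist or exercise physiologist (Protocol 4.7.3), and stopped boys stay in follow-up (3.5.1, 6.12). SAP 6.6.5 summarises iron categories regardless of dosing decisions. Entry requires a normal R2* and limits on iron indices (4.1), so the band rate on placebo may be well under 1%. The E-DMC can end individual review early, cut liver MRI to Visits 19 and 32, or release the iron data if they prove not to be unblinding (3.5, 6.7, 7.7.1). If it closes 20 mg/kg, the asymmetry disappears.

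All of that stands and limits the size of the point. It does not remove the mechanism, which follows from Table 2 and the text after it. Two stronger readings go beyond the documents. A reader might infer that an R2* stop identifies placebo at any review. It does not at Week 13, where the arms are handled alike, nor reliably at Week 45, where active boys reduced earlier can also be stopped. A reader might also take 91% to 100% as a property of the design. That range needs at most 5% of active boys unescalated and equal band rates. The documents give neither, and equal rates are a weak default when 3.5.1 blinds R2* because it may reveal treatment.

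A comforting reading also needs limiting. A placebo boy stopped at Week 29 loses no drug in Period 1 only. Protocol section 5 says "Subjects in Sequence 3 will receive active drug in Period 2 in accordance with the dose adjustment criteria", 3.5.1 terminates his dosing, and I find no restart rule. An active boy with the same scan continues at 5 mg/kg.

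**Conclusion.** The rule undercuts the blind at Week 29. A stop known to be in the band is nearly always placebo if active boys are on schedule: 100% with all escalated, 91% with 5% unescalated and equal rates, 77% with 5% unescalated and a tripled rate, and lower if more boys remain at 5 mg/kg. Allocation alone gives 33%. The percentages rest on assumed f and k; the direction does not, so long as most active boys have escalated.

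This is a minor point. The inference is open mainly to the Medical Monitor, and lasts only while individual review and the Week 29 liver MRI continue and 20 mg/kg stays open. The number of boys is small and unknown. A reader might infer that the primary result is compromised, but with continued follow-up and a separate evaluator, bias in the full-analysis-set stair-climb estimate should be small. I make no claim for Period 2 reviews or for the per-protocol analysis.

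**What to change.** In Protocol 3.5.1, judge Sequence 3 boys in Period 1 against a sham dose level that follows Table 3 and moves by the Table 2 rules, visible only to the Designated Reviewer and the unblinded pharmacist. Leave the R2* thresholds and the mild-overload stop unchanged. Keep the stop for a Sequence 3 boy above normal at Week 45, because active drug is due at Week 49. In the SAP, report R2*-triggered Reduce and Stop decisions together by arm.

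At Week 29 this removes band stops if all boys are on schedule. If 5% lag in both arms, the share returns to 33% at equal rates.

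The cost is wording, one IRT field seen only by unblinded roles, and sham bookkeeping. No visits or scans are added. There are two downsides:
- A placebo boy in the band at Week 29 continues blinded placebo infusions and his Investigator is not told. This already happens to an active boy whose dose is reduced.
- A residual signal remains at Week 45. The share there becomes (1 + s)/(1 + s + 2ks), which is 60% against 50% now at k = 1 and s = 0.5, or 33% against 25% at k = 3. It comes after the last Period 1 dose.

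Withholding R2* from stop notices would not be an adequate substitute. Haematology referral applies only above the mild-overload threshold (Protocol 7.9), so a stop without referral would still mark the band.
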